Official title: Mindfulness-Based Intervention for Caregivers of Frail older adults:
Towards a model of intergenerational caregiving for Chinese families

NCT number: to be assigned

Document date: April 22, 2021

The research questions of the proposed study are:

- 1) investigate the effects of a brief mindfulness-based intervention for caregivers of frail elders in reducing caregiver burden and depression;
- 2) compare the effects of mindfulness-based intervention with an evidence-based caregiver programme; and
- 3) explore the factors that contribute to the positive improvements of both caregiver programmes, and develop a preliminary model for understanding and reducing caregiver burden and depression.

RESEARCH PLAN AND METHODOLOGY

Study design

In view of the research objectives about efficacy of the MBI and in the interest of developing a model of mediators in the MBI and intergenerational caregiving, a multi-site, three-arm, randomized controlled trial will be implemented (Baron et al., 2013). The effects of the MBI for caregivers for frail elderly will be tested by comparing the MBI (Arm 1), with psychoeducation (Arm 2), and treatment-as-usual (Arm 3). Assessments will be scheduled pre-intervention (T0), post-intervention (T1), and at 6-month follow-up (T2). The program effects will be tested using both pairwise between-subject comparisons (Arm 1 vs Arm 2, Arm 2 vs Arm 3, and Arm 1 vs Arm 3) and within-subject comparisons (measures at T0, T1, and T2). The between-group analyses will be adjusted for baseline scores and for factors related to outcomes, including the age and sex of the caregivers, the severity of depression, anxiety, caregiver burden, and the level of frailty of elderly. Refinement of design from a pilot study. A pilot study has been conducted in August to September 2019.

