Sample size estimation. We calculated the sample size needed for the first two hypotheses and choose the larger one for the estimation of overall sample size. For the first hypothesis, the calculation is based on a previous study of an MBI for caregivers (Hou et al., 2014), in which an effect size of 0.64 in depression, with an estimation of an effect size of 0.14 for Arm 3. For a two-tailed α error of 5%, an 80% power, and a test of three independent groups, the required sample size will be 64 per arm (Cohen, 1988). For the second hypothesis, the calculation is based on a non-inferiority comparison was conducted. A non-inferiority margin of 50%, as common practice in non-inferiority trials (Althunian et al., 2017), is selected and the required sample size will be 51 per arm. We further adjust the sample size based on an estimation of drop-out rate and intra-class correlation. An estimation of a drop-out rate of 15% is based on two local studies of mindfulness-based intervention (Hou et al., 2014; Lo et al.,

2015). Besides, an estimation of intra-class correlations of 0.07 is based on PI's two recent mindfulness multi-site studies ranged from 0 to 0.07 (Lo et al., 2017; Lo et al., in press), and 240 caregivers will be recruited for this study. Based on such estimation, it should also be necessary to conduct mediational studies with .8 statistical power (Fritz & MacKinnon, 2007).

Recruitment of participants. The inclusion criteria for participation in this study are: 1) Caregivers of frail elderly based on a professional's assessment of Clinical Frailty Scale with a score of 6, indicating a moderate level of frailty or above (Rockwood et al., 2005). 2) Caregivers being adult children or children in-law of the elder care receiver. 3) Caregivers who are experiencing caregiver burden at the time of study, with scores of 8 or above in ZBI-4 (Bedard et al., 2001). The exclusion criteria include: 1) Caregivers who have diagnoses of psychosis, developmental disabilities, or cognitive impairment, which may present difficulties in comprehending the content of the program. 2) Spouses, siblings, or friends will be excluded as their burden or depressive symptoms may be attributed to different reasons. 3) Caregivers of elders with moderate to severe dementia will be excluded and the Clinical Dementia Rating Scale will be administered (Huges et al., 1982), and 4) Caregivers who had participated in a MBSR or equivalent.

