All analyses will be carried out according to the intention-to-treat approach and all participants who receive randomization and allocation to one of three treatment arms will be included for analyses (Moher et al., 2010). Repeated measure ANOVA will be used to evaluate the effects of the MBI (Arm 1), relative to PSY (Arm 2) and TAU (Arm 3), and the analyses of the primary and secondary outcome measures will be analyzed. In addition to the immediate programme effects, outcomes measured at T1 and T2 will be compared, to assess whether maintenance effects will be sustained at 6-months.

The mediation effects on the relationships between group (MBI or PSY vs. TAU)

variables and caregiver outcome variables (ZBI, CES-D, HAD-A), controlling the baseline variables (sex and age of caregivers, frailty score), will be evaluated using the PROCESS macro in SPSS (Hayes, 2012), in order to compute the effect of the independent variable on the mediator (a), the effect of the mediator on the dependent variable (b), total effect (c), direct effect (c'), and bootstrapped (i.e., 10,000 random samples) bias-corrected 95% confidence intervals of the indirect effect (ab).

According to Hayes (2009), with significant paths a and b, even without a significant path c, confidence intervals that do not include zero indicate a significant indirect (i.e., mediation) effect.

Appendix 1
Recruitment Flowchart

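### The plan promises to analyse every randomised caregiver, but its repeated-measures ANOVA in standard form keeps only complete records and no missing-data method is given

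*Combined protocol and SAP*

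**What the plan says.** The Data Analyses section adopts intention to treat and says that "all participants who receive randomization and allocation to one of three treatment arms will be included for analyses". The next sentence gives the method: "Repeated measure ANOVA will be used to evaluate the effects of the MBI (Arm 1"), relative to the other two arms, for the primary and secondary outcomes. The same section adds that "outcomes measured at T1 and T2 will be compared, to assess whether maintenance effects will be sustained at 6-months".

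The Study design section schedules assessments at T0, T1 and T2, lists within-subject comparisons across all three, and says that between-group analyses adjust for baseline scores and other covariates.

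Under Sample size estimation, "An estimation of a drop-out rate of 15% is based on two local studies of mindfulness-based intervention", and "240 caregivers will be recruited for this study".

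The plan does not mention missing data, imputation, carry-forward, a mixed model or a missing-data sensitivity analysis. The mediation models, run with the PROCESS macro, have no missing-data rule either.

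**The concern.** Repeated-measures ANOVA in its standard form needs a full row per person. A caregiver with T0 and T1 but no T2 drops out of a three-time-point analysis altogether, and the T1 score goes too. With drop-out expected, the promised analysis set and the named method cannot both hold unless a further step is added, and none is stated.

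What is at stake is the validity of the between-arm comparison. Arms 1 and 2 ask for four sessions and 15 minutes of daily home practice, while Arm 3 receives standard care. Reasons for leaving could therefore differ by arm. If caregivers who are not improving tend to leave an active arm, removing them flatters that arm at T1. The T1-to-T2 maintenance comparison would also rest on those who stayed.

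**Working it through.** **1. The plan's own figure.** Inputs from Sample size estimation: effect sizes 0.64 and 0.14, two-sided 5%, 80% power. The difference is d = 0.64 - 0.14 = 0.50. The normal formula, n = 2(1.96 + 0.84)²/0.50², gives 63 per arm. The t-test version gives 63.8, so 64. The stated 64 per arm is reproduced.

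**2. From 64 to 240.** Drop-out alone gives 64/0.85 = 75.3, so 76 per arm and 3 × 76 = 228. Multiplying also by 1.07 gives 64 × 1.07/0.85 = 80.6, so 81 per arm and 243, close to 240. That reading of the intra-class correlation adjustment is inferred. Either way, drop-out is already allowed for.

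**3. Who is left out.** 0.15 × 240 = 36, leaving 204. With equal allocation (assumed; the ratio is not stated), that is 12 lost and 68 analysed per arm. Two-group t-test power at d = 0.50, ignoring clustering, is 82% with 68 per arm and 88% with 80.

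**4. Does the method exclude incomplete records?** A standard repeated-measures ANOVA routine (in Python statsmodels) was given data in which some subjects lacked the third time point. It stopped with an unbalanced-data error. The planned software could instead drop such subjects, but it would not use them without an added step.

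**5. Possible bias at T1, by simulation.** All settings here are assumptions: two arms of 80, no true effect, unit variance, correlation 0.5 or 0.7 between times, 15% lost in each arm, baseline-adjusted T1 contrast, 4,000 runs per setting. Outcome-dependent loss means that loss after T1 is more likely after a worse T0-to-T1 change, with odds ratio 2.0, 2.7 or 7.4 per SD. Bias is in favour of the active arm.

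| Drop-out mechanism | OR 2.0 | OR 2.7 | OR 7.4 |
|---|---|---|---|
| All loss after T1, outcome-dependent in both arms alike | within 0.003 SD; error about 5% | same | same |
| Half before T1 at random; half after T1, outcome-dependent in active arm only | 0.03-0.04 SD; about 6% | 0.05 SD; 6-7% | 0.07-0.09 SD; 9-10% |
| All after T1, outcome-dependent in active arm only | 0.06-0.07 SD; 8-9% | 0.09-0.10 SD; 10-11% | 0.14-0.16 SD; 19-21% |

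In the bottom-row setting, using every observed T1 score gave bias within 0.003 SD and error of 4.7-5.6%.

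**6. A second simulation, with a true T1 effect of -0.50** (correlation 0.6, 80 per arm, about 10-11% lost after T1). The completer estimate was -0.50 with random loss, -0.49 when loss depended on T1 score alike in both arms, and -0.58 when the dependence ran in opposite directions by arm. Using all observed data gave -0.50 each time.

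**The case against.** The strongest reply is that deletion of T1 scores is inferred. The Data Analyses section does not say which time points enter the ANOVA. It treats the T1-to-T2 comparison as additional to the immediate effects, and the Study design section speaks of adjusting for baseline. If immediate effects are tested on T0 and T1 only, a caregiver lost after T1 keeps the T1 score in that test. This stands as a limit. But the Study design section also lists within-subject measures at all three times, and even a two-time-point ANOVA leaves out anyone lost before T1, so the conflict with the promised analysis set remains.

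Three further points also stand:

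- Drop-out is not split by arm or into before and after T1, and no mechanism is given. The biases above are conditional, and one plausible case shows none.
- The good performance of the all-observed analysis is partly built in, because loss in the simulations depends only on observed scores. Caregivers who leave before T1 because they are doing badly could bias a mixed model too.
- Coupons for completing T1 and T2 may reduce loss, though they do not handle it in the analysis.

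An imputation step that the plan does not state could reconcile the two sentences. Leaving it unstated keeps the choice open until the data have been seen.

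**Conclusion.** The point holds as a conflict between the promised analysis set and the named method, with up to 36 of 240 caregivers affected. The result would be a completer analysis labelled intention to treat. Its bias at T1 runs from about 0 to about 0.16 SD, with error from about 5% to 21%, depending on drop-out patterns that the documents do not give. It should be fixed before analysis.

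A reader might infer more, in four ways that the documents do not support:

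- **All 36 lose an observed T1 score.** Only those lost between T1 and T2 have one to lose, and their number is not given.
- **Bias in favour of the programme is established.** It arises only if outcome-dependent loss differs by arm.
- **The trial falls short of its own sample size.** 68 completers per arm exceeds the plan's 64, with equal allocation and clustering ignored.
- **A three-time-point ANOVA would lose all of Arm 3**, because the Implementation and assessment text describes T2 for Arms 1 and 2 only. The Study design section schedules T2 for the whole trial. The two places need reconciling, but they do not show that Arm 3 has no T2.

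**What to change.** In the Data Analyses section, replace the repeated-measures ANOVA with a likelihood-based linear mixed model for repeated measures. Its terms are arm, time, arm-by-time, baseline score and the covariates listed under Study design. Fit it to every observed score of every randomised caregiver, and take the T1, T2 and T1-to-T2 contrasts from that one model. Multiple imputation before the planned analysis is an acceptable alternative.

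Add a sensitivity analysis for data not missing at random. Run the mediation models on multiply imputed data, or label them as completer analyses.

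The cost is revised wording and slightly more analysis work, with no extra participants or visits. The main analysis would rely on data being missing at random. That is weaker than what a completer ANOVA needs, but still untestable, hence the sensitivity analysis.

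### The planned ANOVA has no therapy-group term although Arms 1 and 2 are delivered in groups; if the plan's ICC of 0.07 applies to those groups, nominal 5% between-arm tests err about 9% to 15%

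*Combined protocol and SAP*

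**What the plan says.** **Analysis.** The Data Analyses section names one method for the primary and secondary outcomes: "Repeated measure ANOVA will be used to evaluate the effects of the MBI (Arm 1), relative to PSY (Arm 2) and TAU (Arm 3". The Study design section lists the adjustment factors: baseline scores, caregiver age and sex, severity of depression, anxiety and burden, and frailty of the elder. The mediation analysis uses the PROCESS macro and controls for sex, age and frailty. None of these has a term for therapy group or site. (The figure at the start of Data Analyses was not available; this statement covers the text.)

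**Delivery.** Under Procedures, Arms 1 and 2 run as groups of 10 to 15 caregivers in the units of four NGOs and a university. Arm 3 receives standard care and has no groups.

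**Sample size.** The first hypothesis uses "an effect size of 0.64 in depression, with an estimation of an effect size of 0.14 for Arm 3", and "the required sample size will be 64 per arm". For the second, "the calculation is based on a non-inferiority comparison was conducted", giving 51 per arm. The plan then allows for 15% drop-out and for "an estimation of intra-class correlations of 0.07". The source of that value is "two recent mindfulness multi-site studies ranged from 0 to 0.07". The result is that "240 caregivers will be recruited for this study".

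**The concern.** Participants in one therapy group share an instructor, sessions and each other, so their outcomes after T0 may be correlated. The plan allows for an ICC when it counts participants but not when it analyses them. A test that treats grouped people as independent understates the standard error and declares differences too often. A larger sample restores power but does not correct that error rate. Baseline adjustment does not remove it either, because randomisation follows T0 and the groups form later.

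All three pairwise comparisons involve at least one grouped arm. MBI vs PSY is hit hardest because both arms are grouped. If it is the non-inferiority comparison, the same fault means declaring non-inferiority too often. The total effect in the mediation analysis is a between-arm test with the same gap.

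**Working it through.** **Inputs.** From Sample size estimation: two-sided 5%, 80% power, effects 0.64 and 0.14 (difference 0.50 SD), 64 and 51 per arm, 15% drop-out, ICC 0.07 at the top of a 0 to 0.07 range, total 240. From Procedures: groups of 10 to 15 in Arms 1 and 2. Assumed, because the allocation ratio is not stated: 80 per arm. Eighty people then make 8 groups of 10 down to 6 groups averaging 13.33 (five groups of 15 hold only 75).

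**The plan's own figures.** 2(1.96 + 0.84)²/0.50² gives 63 per arm, and the t distribution gives 64, so 64 reproduces. A one-sided 5% t test against a margin of 0.5 SD gives 51, but the plan states neither the one-sided level nor the scale of the margin. For the total, 64 × 1.07/0.85 = 80.6 per arm, about 242. So 240 fits an inflation of about 1.07. That is an inference, since no formula or cluster size is given.

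**Error of a test that ignores groups.** DE = 1 + (m − 1) × ICC. The variance inflation v is DE when both arms are grouped and (DE + 1)/2 when only one is. Actual two-sided error = 2[1 − Φ(1.96/√v)]. PSY vs TAU behaves as MBI vs TAU.

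| Group ICC | m | DE | MBI vs PSY | (DE + 1)/2 | MBI vs TAU |
|---|---|---|---|---|---|
| 0.07 | 10 | 1.63 | 12.5% | 1.315 | 8.7% |
| 0.07 | 13.33 | 1.863 | 15.1% | 1.432 | 10.1% |
| 0.035 | 10 | 1.315 | 8.7% | 1.158 | 6.85% |
| 0.035 | 13.33 | 1.432 | 10.1% | 1.216 | 7.55% |
| 0.02 | 10 | 1.18 | 7.1% | 1.09 | 6.0% |
| 0.02 | 13.33 | 1.247 | 7.9% | 1.123 | 6.4% |
| 0 | any | 1 | 5% | 1 | 5% |

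After 15% drop-out (m = 8.5 to 11.33), ICC 0.07 gives 11.2% to 13.5% and 8.1% to 9.3%. Simulated t tests with 80 per arm at ICC 0.07 gave 12.5% to 15.4% and 8.7% to 10.3%.

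**Non-inferiority, MBI vs PSY, ICC 0.07, 80 per arm.** Error at the margin is 1 − Φ(1.645/√DE) = 9.9% to 11.4% for a one-sided 5% test. With 1.96 in place of 1.645 (one-sided 2.5%) it is 6.2% to 7.6%.

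**Group-by-time F test, ICC 0.07, simulated, complete data.** With an assumed between-visit correlation of 0.5: 11.7% to 15.0% (MBI vs PSY) and 8.4% to 9.7% (MBI vs TAU). Over correlations of 0.3 to 0.7, which the documents do not give: 10.3% to 21.3% and 7.4% to 13.3%.

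**T1 vs T2.** A group effect that is equal at both visits cancels in the T2 − T1 difference. Simulated error for the between-arm comparison of that difference at ICC 0.07 was 4.6% to 5.4%.

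**Sample size, like for like after drop-out.** 80 × 0.85 = 68 per arm. At a group ICC of 0.07, DE is 1 + 7.5 × 0.07 = 1.525 to 1 + 10.33 × 0.07 = 1.723.
- MBI vs TAU: room for 68/64 = 1.06; needed (DE + 1)/2 = 1.26 to 1.36.
- MBI vs PSY: room for 68/51 = 1.33; needed 1.53 to 1.72.

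At ICC 0.02 the needs are 1.08 to 1.10 (just above 1.06) and 1.15 to 1.21 (within 1.33).

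**Power, MBI vs TAU at 0.50 SD.** Φ(0.50/√(2v/68) − 1.96) is 83% with v = 1. At v = 1.26 to 1.36 it is 74% to 70%, before any gain from baseline adjustment or loss from few degrees of freedom.

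**The case against.** The strongest objection is that 0.07 may not be a therapy-group value. It comes from multi-site studies, is the top of a range that starts at 0, and has no stated level. If it is wholly a site ICC and individually randomised arms are spread over sites, the ANOVA has no inflation. A model with a group term but no site term would then be too cautious: in a simple test on group means (8 groups of 10 per arm, balanced over four sites, 0.07 all at site level), error was about 2.0% without a site term and about 5.0% with one. This stands. It makes the size of the harm conditional and puts site into the fix.

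A reader might set the room of 1.06 against a design effect of 1.63 to 1.86 and conclude that the sample is far too small. The documents do not support this. The 1.06 comes from 64 per arm, sized for MBI against ungrouped TAU, while 1.63 to 1.86 is the MBI vs PSY inflation before drop-out. Compared like for like, the shortfall at ICC 0.07 is smaller. The baseline adjustment promised under Study design may recover part of it, depending on a correlation that is not given.

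A reader might also infer that every planned comparison is inflated. The maintenance comparison of T1 with T2 is not, if the group effect is the same at both visits.

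**Conclusion.** The omission is real: outcomes are collected in therapy groups, an ICC is budgeted for, and no described analysis uses it. If 0.07 holds at therapy-group level, with 80 per arm in 6 to 8 groups, a nominal two-sided 5% test of one post-baseline score errs 12.5% to 15.1% (MBI vs PSY) and 8.7% to 10.1% (MBI vs TAU). Half that ICC gives about 9% to 10% and 7% to 7.5%. The effect covers between-arm tests at T1 or T2, group-by-time tests from baseline, and the mediation paths that compare arms.

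It would be tempting to say flatly that this trial's tests err at 12% to 15%. The documents do not support that, because they do not identify the level of the ICC and their own range includes 0. At a group ICC of 0.07 the sample is short for both contrasts, but the MBI vs PSY figure assumes that this is the second hypothesis; the hypotheses are not listed, and only the second research question points that way. The point should be fixed, but its size is uncertain, so it is not ranked as a mandatory correction.

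**What to change.** **Data Analyses.** Replace the repeated-measures ANOVA by a linear mixed model with:
- T0, T1 and T2 as outcomes, baseline means equal across arms, and arm-by-time effects;
- unstructured participant-level covariance;
- a fixed effect for site;
- a random effect for therapy group at T1 and T2 in Arms 1 and 2 only, with TAU participants as singletons;
- Satterthwaite or Kenward-Roger degrees of freedom;
- the Study design covariates, except the baseline of the outcome being analysed, which is already in the model.

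Use this model's interval for the non-inferiority comparison and state the one-sided level. Give the mediation paths the same terms, or report them as not allowing for clustering.

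**Data collection.** Record site for everyone, and the allocated therapy group for everyone randomised to Arms 1 and 2, including people who never attend.

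**Sample size estimation.** State whether 0.07 is a site or therapy-group ICC, and restate the power for each contrast.

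**Secondary.** Study design schedules T2 without exception and Recruitment of participants refers to T2 for Arm 3, but Implementation and assessment describes T2 as the final assessment for Arms 1 and 2. The last is ambiguous rather than a denial. The sections must be reconciled, since TAU contrasts at T2 depend on it.

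**Cost.** No new participants or visits. Between-group degrees of freedom are few: 2 × 6 − 2 = 10 to 2 × 8 − 2 = 14 for MBI vs PSY, before the site effect. In simulated fits of this model with Satterthwaite degrees of freedom but without site or other covariates (correlation 0.5, 15% drop-out), the 95% half-width at T2 rose from 0.29 SD to 0.34–0.36 (MBI vs TAU) and 0.39–0.43 (MBI vs PSY) at ICC 0.07, or to 0.31 and 0.33–0.34 at ICC 0.02. Two-sided error was 4.4% to 6.4% at ICC 0.07 and 3.6% to 4.6% at ICC 0, so the model is slightly conservative if groups do not matter. Kenward-Roger was not tried.

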Caregiver burden - Measured by 22-item Zarit Burden Interview (ZBI) (Zarit et al., 1980)	$\alpha = .88$ (Tang et al., 2017)
Secondary outcome variables	
Depressive symptoms - measured by 10-item The Center for Epidemiologic Studies Depression Scale (CES-D) (Radloff, 1977)	$\alpha = 0.78$ (Boey, 1999)
Anxiety symptoms - measured by 7-item Hospital Anxiety and Depression Scale – Anxiety subscale (HAD-A) (Zigmond & Snaith, 1983)	$\alpha = 0.77$ to 0.82 (Leung et al., 1999)
Positive caregiving experiences - Measured by 9-item Positive Aspects of Caregiving Scale (PAC) (Tarlow et al., 2004)	$\alpha = 0.89$ (Lou et al., 2015)
Spiritual well-being - measured by 12-item Functional Assessment of Chronic Illness Therapy–Spiritual Well-Being Scale (FACIT-Sp-12) (Peterman et al., 2002), with two subscales in meaning/peace and faith	$\alpha = 0.80$ (Wang, 2016)
Family conflicts - measured by 10-item Revised Conflict Tactics Scale (CTS2) (Beach et al., 2005), with subscales in psychological mistreatment (5 items) and physical abuse (5-items)	$\alpha = .81$ to $.82$ (Yan & Tang, 2001)
Biomarker: Heart rate variability - measured by the CorSense Heart Rate Variability monitor	N.A.
Mediators of outcome	
Cognitive factor: Coping styles - measured by 28-item brief COPE (Carver, 1997), with 11 subscales (problem-solving, accommodation, support-seeking, behavioral disengagement, denial, self-distraction, self-blame, humour, venting, substance use, and religion)	$\alpha = 0.76$ for whole scale, and $\alpha = .49$ to $.87$ for subscales (Tang et al., 2016)
Cognitive factor (psychoeducation-specific): Self efficacy - Measured by 5-item subscale of controlling upsetting thoughts (5 items) in the Revised Scale for Caregiving Self-Efficacy (RSCSE) (Steffen et al., 2002)	$\alpha = .86$ (Au et al., 2009)
Cognitive factor (mindfulness-specific): Experiential avoidance - measured by 15-item The Brief Experiential Avoidance (BEAQ) Questionnaire (Gamez et al., 2011)	$\alpha = 0.81$ (Lo et al., in review)

3. Data Analyses

[figure not shown]

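### The plan has no analysis of how many caregivers report physical abuse; if most scores are zero, its comparisons of means can miss or mask a change in that number.

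*Combined protocol and SAP*

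**What the plan says.** Table 1 lists family conflicts as a secondary outcome, measured by the 10-item CTS2 "with subscales in psychological mistreatment (5 items) and physical abuse (5-items"). It gives no scoring rule and does not say whether the two subscales are analysed apart or summed.

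Section 3 (Data Analyses) names one method for outcomes: "Repeated measure ANOVA will be used to evaluate the effects of the MBI (Arm 1), relative to PSY (Arm 2") and TAU (Arm 3). The same sentence adds that "the analyses of the primary and secondary outcome measures will be analyzed", with no exception for any outcome.

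Study design plans "pairwise between-subject comparisons (Arm 1 vs Arm 2, Arm 2 vs Arm 3, and Arm 1 vs Arm 3"), within-subject comparisons over T0, T1 and T2, and this: "The between-group analyses will be adjusted for baseline scores and for factors related to outcomes". It names no further model. Read with section 3, these are also comparisons of mean scores. The mediation analysis covers only ZBI, CES-D and HAD-A.

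No section plans a binary, count or rank-based analysis, or a number or percentage of caregivers reporting abuse. No adverse-event reporting is described.

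**The concern.** The mean of a subscale like this is the share of caregivers who report anything, multiplied by the average score among those who do. When few report, a handful of high scorers dominates both the mean and its variance. Two things can then go wrong. A real change in the number reporting may be lost in noise, whether it is a rise (a harm) or a fall (a benefit). Or a rise in the number reporting may be offset by lower scores among reporters and leave the mean unchanged.

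A reader of the trial report would want to know how many caregivers in each arm reported physical abuse, and how many began to do so after T0. The plan as written produces neither figure. The primary outcome (ZBI) is not affected.

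**Working it through.** **The plan's own figure.** Sample size estimation gives 64 per arm for depression: "in which an effect size of 0.64 in depression, with an estimation of an effect size of 0.14 for Arm 3", that is 0.64 − 0.14 = 0.50 SD, two-sided 5%, 80% power. n = 2 × (1.960 + 0.842)² / 0.50² = 62.8, so 63 by the normal approximation. The t-test gives 63.8, so 64, which reproduces. This figure says nothing about abuse.

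**Number analysed.** 240 / 3 = 80 per arm, assuming equal allocation. With the plan's 15% drop-out, 80 × 0.85 = 68.

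**Assumptions, none of them in the documents.** 10% of caregivers report some physical abuse at T0; the mean score among reporters is 3, right-skewed; latent T0–T1 correlation is 0.6 to 0.7. The check covers one two-arm contrast at T0 and T1, two-sided 5%, with no clustering.

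**Tests compared.**
- Change score: t-test on T1 − T0, identical to the group-by-time F test with two visits.
- Adjusted mean: T1 score regressed on arm and T0 score.
- Any/none at T1: a chi-square test in one simulation; in the other, a linear-probability model adjusted for any/none at T0, standing in for logistic regression.

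**Why masking is possible.** Mean = share reporting × mean score among reporters. At 10% with mean 3: 0.10 × 3 = 0.30. At 30% with mean 1: 0.30 × 1 = 0.30. Reporters triple and the mean does not move.

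**Simulated power, 68 per arm** (a range covers the two simulations; the last two rows come from one)

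| Scenario in one arm | Change score | Adjusted mean | Any/none |
|---|---|---|---|
| 10% to 30%, same severity | 0.52–0.53 | 0.65 | 0.85–0.88 |
| 10% to 30%, severity 3 to 1 | 0.05–0.06 | 0.11 | 0.85–0.88 |
| 10% to 20%, same severity | 0.19 | 0.26 | 0.37 |
| No change, 10% | 0.04 | 0.04 | 0.05 |

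Under no change all tests reject at or below about 5%, so the problem is lost power and masking, not false positives.

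**Check of the any/none figures by formula.** Power = Φ[(Δ − 1.96 × √(2p̄(1 − p̄)/n)) / √((p₁(1 − p₁) + p₂(1 − p₂))/n)].
- 10% v 30%, n = 68: (0.20 − 1.96 × 0.0686) / 0.0664 = 0.987, power 0.84.
- 10% v 20%, n = 68: (0.10 − 1.96 × 0.0612) / 0.0606 = −0.33, power 0.37. At 80 per arm it is 0.42.

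**Sensitivity.** With correlation from 0.3 to 0.8 and mean positive score 2 to 3, the 10% to 30% rise gives 0.42–0.84 (change score), 0.55–0.85 (adjusted mean) and 0.85–0.94 (adjusted any/none). An unadjusted Fisher test gives 0.78–0.81, below the best case for the adjusted mean. The gain is therefore not uniform and owes something to baseline adjustment.

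**The case against.** The strongest reply is that the premise comes from outside the documents. They give no prevalence, item scoring or distribution, and the sample is selected for burden (ZBI-4 of 8 or above), so a low prevalence cannot be taken for granted. That stands, and the point is therefore conditional. Pooled T0 data can settle it.

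Second, the large gains belong to large changes. For 5% to 10%, power is 8% (change score), 12% (adjusted mean) and 18% (adjusted any/none), so every method is close to blind. That also stands. The added analysis reports the right quantity but does not make the trial adequate for it.

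Third, any/none has a blind spot of its own. If 20% report throughout and the mean score among reporters in one arm goes from 3 to 6, the mean-based tests have about 0.20 power and any/none has 0.05. This is a good reason not to replace the mean comparison.

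Some stronger readings are tempting but unsupported:
- *This is the trial's one harm measure.* Psychological mistreatment is in the same scale, and Table 1 does not say who the victim is; that it is the frail elder is inferred from context.
- *Repeated-measures ANOVA is the only analysis.* Study design adds baseline-adjusted comparisons, which do better than the change score though they remain mean-based.
- *A 10-item total will hide abuse behind milder items.* The documents name two subscales and nowhere say that a total is used. The scoring is simply unstated.

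**Conclusion.** The point holds in conditional form. Every analysis the plan names for this outcome compares means, and none reports the number of caregivers with any physical abuse. If most scores are zero, a rise from 10% to 30% would be detected with power of about 0.52 to 0.65 by the planned methods, against 0.85 to 0.88 by any/none. With an offsetting fall in severity, the planned methods detect it 6% to 11% of the time, against about 88%.

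These sizes rest on assumed prevalence, severity and correlation, and on 68 per arm in one two-arm contrast over two visits. They ignore the ICC of 0.07 and the three pairwise comparisons, both of which lower power for all methods. A reader might infer that the planned ANOVA gives false results, or that any/none makes this a powered outcome. Neither follows: error rates under no effect are about nominal or lower, and a change from 10% to 20% has power of only about 0.4 with any/none. This is a gap in a secondary outcome that is worth closing because the remedy is cheap.

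**What to change.** In section 3 (Data Analyses):

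1. State how the CTS2 is scored, and that physical abuse is analysed separately from psychological mistreatment.
2. Keep the planned mean comparison for the subscale.
3. Add, by arm and visit, the number and percentage of caregivers endorsing any physical-abuse item, and the number newly reporting among those with none at T0.
4. Add a between-arm risk difference with 95% CI at T1 and T2, using logistic regression adjusted for any/none at T0 (Firth-penalised or exact if events are sparse).
5. State that the trial is not powered for modest changes on this outcome.

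The cost is SAP wording, one model and one table from data already collected, with no new visit, instrument or staff. Fixing this before unblinding also prevents a later choice between total, subscale and any/none. The drawback is one more analysis of a secondary outcome, and one that does not register a change in frequency among existing reporters; the retained mean comparison covers that.
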